8.3.2.1. Hypoglycemia

Upon ICF signing, all participants will be educated about signs and symptoms of hypoglycemia and how to treat hypoglycemia. Participants will be asked to contact site personnel if they experience any of these symptoms.

Hypoglycemia may be identified by spontaneous reporting of symptoms from participants (whether confirmed or unconfirmed by simultaneous glucose values) or by blood glucose (BG) samples collected during study visits.

All participants who develop incident diabetes during the study will be provided with glucometers. Participants without diabetes may, at the investigator's discretion, be given glucometers to assist in the evaluation of reported symptoms consistent with hypoglycemia. Participants receiving glucometers will be provided a diary to record relevant information (for example, glucose values and symptoms).

Participants who develop incident diabetes during the study may be started on allowed glucose-lowering medications (Section 6.5.2). In the event that participants subsequently develop persistent or recurrent unexplained hypoglycemia during the treatment period, participants will be asked to reduce the dose or discontinue any concomitant glucose-lowering medication commonly associated with hypoglycemia (for example, sulfonylurea or insulin).

All hypoglycemic episodes will be recorded on a specific eCRF and should not be recorded as AEs unless the event meets serious criteria. If a hypoglycemic event meets severe criteria (see definition below), it should be recorded as serious on the AE and SAE eCRFs, and reported to Lilly as an SAE.

Investigators should use the following definitions and criteria when diagnosing and categorizing an episode considered to be related to hypoglycemia (the BG values in this section refer to values determined by a laboratory or International Federation of Clinical Chemistry and Laboratory Medicine blood-equivalent glucose meters and strips) in accordance with the 2020 American Diabetes Association position statement on glycemic targets (ADA 2020). **Level 2** and **Level 3** hypoglycemia events are considered as adverse events of special interest:

Level 1 hypoglycemia:

Glucose <70 mg/dL (3.9 mmol/L) and ≥54 mg/dL (3.0 mmol/L): Level 1 hypoglycemia can alert a person to take action such as treatment with fast-acting carbohydrates. Providers should continue to counsel participants to treat hypoglycemia at this glucose alert value.

Level 2 hypoglycemia:

Glucose <54 mg/dL (3.0 mmol/L): This is also referred to as documented or BG-confirmed hypoglycemia with glucose <54 mg/dL (3.0 mmol/L). This glucose threshold is clinically relevant regardless of the presence of absence of symptoms of hypoglycemia.

Level 3 hypoglycemia:

Severe hypoglycemia (in adults): A severe event characterized by altered mental and/or physical status requiring assistance for treatment of hypoglycemia. For example, participants had altered mental status and could not assist in their own care, or were semiconscious or unconscious, or experienced coma with or without seizures, and the assistance of another person was needed to actively administer carbohydrate, glucagon, or other resuscitative actions. Glucose measurements may not be available during such an event, but neurological recovery attributable to the restoration of glucose concentration to normal is considered sufficient evidence that the event was induced by a low glucose concentration.

- The determination of a hypoglycemic event as an episode of severe hypoglycemia, as defined above, is made by the investigator based on the medical need of the participant to have required assistance and is not predicated on the report of a participant simply having received assistance.
- If a hypoglycemic event meets the criteria of severe hypoglycemia, the investigator must record the event as serious on the AE CRF and report it to Lilly as an SAE.

Nocturnal hypoglycemia:

Nocturnal hypoglycemia is a hypoglycemia event (including severe hypoglycemia) that **occurs at night** and presumably during sleep.

To avoid duplicate reporting, all consecutive BG values <70 mg/dL (3.9 mmol/L) occurring within a 1-hour period may be considered to be a single hypoglycemic event (Weinberg et al. 2010; Danne et al. 2013).

8.3.2.2. Pancreatitis***Diagnosis of Acute Pancreatitis***

Acute pancreatitis is an AE of interest in all studies with LY3437943, including this study. The diagnosis of acute pancreatitis requires 2 of the following 3 features (Banks and Freeman 2006, Koizumi 2006):

- abdominal pain, characteristic of acute pancreatitis (that is, epigastric pain radiating to the back, often associated with nausea and vomiting)
- serum amylase (total, pancreatic, or both) and/or lipase $\geq 3X$ ULN, and
- characteristic findings of acute pancreatitis on CT scan or MRI.

If acute pancreatitis is suspected, the investigator should ensure that the following steps are taken:

- obtain appropriate laboratory tests, including pancreatic amylase (p-amylase) and lipase, and
- perform imaging studies, such as abdominal CT scan with or without contrast, or abdominal MRI.

Note: Abdominal ultrasound may be used as an alternative method only if CT and MRI cannot be performed.

- evaluate for possible causes of acute pancreatitis, including alcohol use, gallstone/gall bladder disease, hypertriglyceridemia, and concomitant medications.

Discontinuation for Acute Pancreatitis

If acute pancreatitis is suspected by the investigator, the participant must temporarily discontinue use of the study drug. Afterwards, if the case is confirmed as acute pancreatitis by the adjudication committee, study drug must be permanently discontinued; the participant may continue in the study. If the case is not confirmed, then the participant can restart study drug, if the investigator deems as clinically appropriate, as described in the Section 6.6.

Case Adjudication and Data Entry

An independent CEC will adjudicate all suspected cases of acute pancreatitis. Relevant data from participants with acute pancreatitis will be entered into a specifically designed eCRF page. The adjudication committee representative will enter the results of adjudication in a corresponding eCRF page.

Asymptomatic Elevation of Pancreatic Amylase and/or Lipase

Serial measures of pancreatic enzymes have limited clinical value for predicting episodes of acute pancreatitis in asymptomatic participants (Nauck et al. 2017; Steinberg et al. 2017a, 2017b). Therefore, further diagnostic follow-up of cases of asymptomatic elevation of pancreatic enzymes (lipase and/or p-amylase $\geq 3X$ ULN) is not mandated but may be performed based on the investigator's clinical judgment and assessment of the participant's overall clinical condition.

8.3.2.3. Thyroid Malignancies and C-Cell Hyperplasia

Individuals with personal or family history of MTC and/or MEN-2 will be excluded from the study. Participants who are diagnosed with MTC and/or MEN-2 during the study will have study drug stopped and should continue follow-up with an endocrinologist.

The assessment of thyroid safety during the trial will include reporting of any case of thyroid malignancy (including MTC, papillary carcinoma, and others) and measurements of calcitonin. These data will be captured in specific eCRFs. The purpose of calcitonin measurements is to assess the potential of LY3437943 to affect thyroid C-cell function, which may indicate development of C-cell hyperplasia and neoplasms.

8.3.2.3.1. Calcitonin Measurements

If an increased calcitonin value (see definitions below) is observed in a participant who has been administered a medication that is known to increase serum calcitonin, then this medication should be stopped, and calcitonin levels should be measured after an appropriate washout period.

For participants who require additional endocrine assessment because of increased calcitonin concentration as defined in this section, data from the follow-up assessment will be collected in the specific section of the eCRF.

Calcitonin Measurements in Participants with eGFR ≥ 60 mL/min/1.73 m²

A significant increase in calcitonin for participants with eGFR ≥ 60 mL/min/1.73 m² is defined below. If a participant's laboratory results meet these criteria, these clinically significant laboratory results should be recorded as an AE.

- *Serum calcitonin value ≥ 20 ng/L and < 35 ng/L AND $\geq 50\%$ increase from the screening value.* These participants will be asked to repeat the measurement within 1 month. If this repeat value is increasing ($\geq 10\%$ increase), the study drug should be stopped, and the participants encouraged to undergo additional endocrine assessment and longer-term follow-up by an endocrinologist to exclude any serious adverse effects on the thyroid.
- *Serum calcitonin value ≥ 35 ng/L AND $\geq 50\%$ over the screening value.* In these participants, study drug should be stopped, and the participants recommended to immediately undergo additional endocrine assessments and longer-term follow-up by an endocrinologist.

Calcitonin Measurement in Participants with eGFR < 60 mL/min/1.73 m²

A significant increase in calcitonin for participants with eGFR < 60 mL/min/1.73 m² is defined as a *serum calcitonin value ≥ 35 ng/L AND $\geq 50\%$ over the screening value.* If a participant's labs meet these criteria, these clinically significant labs should be recorded as an AE.

In these participants, study drug should be discontinued (after first confirming the value) and the participants recommended to immediately undergo additional endocrine assessments and longer-term follow-up by an endocrinologist to exclude any serious adverse effect on the thyroid.

8.3.2.4. Major Adverse Cardiovascular Events

Nonfatal cardiovascular AEs will be adjudicated by a committee of physicians external to Lilly with cardiology expertise. This committee will be blinded to treatment assignment. The nonfatal cardiovascular AEs to be adjudicated include

- myocardial infarction
- hospitalization for unstable angina
- hospitalization for heart failure
- coronary interventions (such as coronary artery bypass graft or percutaneous coronary intervention), and
- cerebrovascular events, including cerebrovascular accident (stroke) and transient ischemic attack.

8.3.2.5. Deaths

All deaths will be adjudicated by a committee of physicians external to Lilly. This committee will be blinded to treatment assignment.

8.3.2.6. Supraventricular Arrhythmias and Cardiac Conduction Disorders

Treatment-emergent cardiac conduction disorders will be further evaluated. Participants who develop any event from these groups of disorders should undergo an ECG, which should be submitted to the central reading center. Additional diagnostic tests to determine exact diagnosis should be performed, as needed. The specific diagnosis will be recorded as an AE. Events that meet criteria for serious conditions as described in Section 10.4 (Appendix 4) must be reported as SAEs.

8.3.2.7. Hypersensitivity Reactions

Many drugs, but particularly biologic agents, carry the risk of systemic hypersensitivity reactions. If such a reaction occurs, additional data describing each symptom should be provided to the sponsor in the eCRF.

Sites should have appropriately trained medical staff and appropriate medical equipment available when study participants are receiving study drug. It is recommended that participants who experience a systemic hypersensitivity reaction be treated per national and international guidelines.

In the case of generalized urticaria or anaphylaxis, additional blood and urine samples should be collected as described in Section 10.3 (Appendix 3). Laboratory results are provided to the sponsor via the central laboratory.

8.3.2.8. Injection Site Reactions

Symptoms of a local injection site reaction may include erythema, induration, pain, pruritus, and edema. If an injection site event is reported, the AE will be recorded, and additional data will be provided to the sponsor in the eCRF. At the time of AE occurrence of severe or serious types, samples will be collected for measurement of LY3437943 antidrug antibodies (ADAs) and LY3437943 concentration.

8.3.2.9. Antidrug Antibodies

The occurrence of ADA formation will be assessed as outlined in Section 8.9.

8.3.2.10. Hepatobiliary Disorders

All events of treatment-emergent (TE) biliary colic, cholecystitis, or other suspected events related to gallbladder disease should be evaluated and additional diagnostic tests performed, as needed. In cases of elevated liver laboratory tests, hepatic monitoring should be initiated as outlined in Section 8.2.5.1.

8.3.2.11. Severe Gastrointestinal Adverse Events

LY3437943 may cause severe GI AEs, such as nausea, vomiting, and diarrhea. Information about severe GI AEs as well as antiemetic/antidiarrheal use will be collected in the eCRF/AE

and Concomitant Medications forms, respectively. For detailed information concerning the management of GI AEs, please refer to Section 6.5.1.

8.3.2.12. Acute Renal Events

Renal safety will be assessed based on repeated renal functional assessment as well as assessment of AEs suggestive of acute renal failure or worsening of preexisting chronic renal failure. Gastrointestinal AEs have been reported with LY3437943, including nausea, diarrhea, and vomiting. This is consistent with other GLP-1R agonists (Aroda and Ratner 2011). These events may lead to dehydration, which could cause a deterioration in renal function, including acute renal failure. Participants should be advised to notify investigators in case of severe nausea, frequent vomiting, or symptoms of dehydration.

8.3.2.13. Depression, Suicidal Ideation, or Behavior Monitoring

Participants will be monitored for depression and suicidal ideation or behavior through AE collection and by using the C-SSRS and the PHQ-9 questionnaires. Scores of the questionnaires must be reviewed by the investigator at the time of each visit and appropriate actions as described below should be taken.

Columbia Suicide-Severity Rating Scale (C-SSRS) is a scale that captures the occurrence, severity, and frequency of suicidal ideation and behavior during the assessment period via a questionnaire. The scale was developed by the National Institute of Mental Health (NIMH) trial group (TASA) for the purpose of being counterpart to the Columbia Classification Algorithm of Suicide Assessment (C-CASA) categorization of suicidal events. For this study, the C-SSRS is adapted for the assessment of the ideation and behavior categories only. The Intensity of Ideation and Lethality of Behavior sections are removed.

The PHQ9 questionnaire is a validated, participant-completed 9-item depression module of the Patient Health Questionnaire, which is used as a diagnostic instrument for common mental disorders. The PHQ-9 consists of 9 items each scored on a scale of 0 = “not at all” to 3 = “nearly every day” with a recall period of “the last 2 weeks.” Major depression is diagnosed if 5 or more of the 9 depressive symptom criteria have been present at least “more than half the days” in the past 2 weeks, and 1 of the symptoms is depressed mood or anhedonia. As a severity measure, a higher score indicates greater severity.

Participants will be referred to a MHP if in the opinion of the investigator it is necessary for the safety of the participant or if the participant had any of the following:

- a PHQ-9 score ≥ 15
- C-SSRS responses of
 - A “yes” answer to Question 4 (Active Suicidal Ideation with Some Intent to Act, Without Specific Plan) on the “Suicidal Ideation” portion of the C-SSRS
 - or**
 - A “yes” answer to Question 5 (Active Suicidal Ideation with Specific Plan and Intent) on the “Suicidal Ideation” portion of the C-SSRS
 - or**

- A “yes” answer to any of the suicide-related behaviors (actual attempt, interrupted attempt, aborted attempt, preparatory act, or behavior) on the “Suicidal Behavior” portion of the C-SSRS

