16. Have obesity induced by other endocrinologic disorders (for example, Cushing's syndrome) or diagnosed monogenetic or syndromic forms of obesity (for example, Melanocortin 4 Receptor deficiency or Prader-Willi Syndrome)
 17. Have a history of significant active or unstable Major Depressive Disorder (MDD) or other severe psychiatric disorder (for example, schizophrenia, bipolar disorder, or other serious mood or anxiety disorder) within the last 2 years
- Note:*** Participants with MDD or generalized anxiety disorder whose disease state is considered stable for the past 2 years and expected to remain stable throughout the course of the study, in the opinion of the investigator, may be considered for inclusion if they are not on excluded medications

18. Have a lifetime history of suicide attempt
19. Have a Patient Health Questionnaire-9 (PHQ-9) score of 15 or more at Visit 1

20. On the C-SSRS at Visits 1, 3, or 4, prior to randomization:
- a “yes” answer to Question 4 (Active Suicidal Ideation with Some Intent to Act, Without Specific Plan) on the “Suicidal Ideation” portion of the C-SSRS
 - or**
 - a “yes” answer to Question 5 (Active Suicidal Ideation with Specific Plan and Intent) on the “Suicidal Ideation” portion of the C-SSRS
 - or**
 - a “yes” answer to any of the suicide-related behaviors (actual attempt, interrupted attempt, aborted attempt, preparatory act, or behavior) on the “Suicidal Behavior” portion of the C-SSRS
- and**
- the ideation or behavior occurred within the past month
21. Have uncontrolled hypertension (systolic BP above or equal to 160 mmHg and/or diastolic BP above or equal to 100 mmHg). If a participant is on anti-hypertensive therapies, doses must be stable for 30 days prior to screening. For participants with uncontrolled hypertension at the screening visit, antihypertensive medication may be started or adjusted. Blood pressure must meet the protocol criterion for hypertension control by Visit 3 with stable treatment for at least 30 days
22. Have an elevated resting pulse rate (>100 bpm) at baseline
23. Have any of the following cardiovascular conditions within 3 months prior to Screening:
- acute myocardial infarction
 - cerebrovascular accident (stroke)
 - unstable angina, or
 - hospitalization due to congestive heart failure (CHF)

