7.1. Discontinuation of Study Intervention

In rare instances, it may be necessary for a participant to permanently discontinue (definitive discontinuation) study drug. If study drug is definitively discontinued, the participant will remain in the study to be evaluated for all planned efficacy and safety measures. In addition, the participant may continue to receive diet and physical activity counseling. Participants who are unwilling to attend all scheduled visits after stopping study drug will be asked to return for a final visit 48 weeks after randomization, primarily for weight measurement and assessment of AEs (Visit 99). If participants are unwilling to attend Visit 99, their refusal to attend should be documented in the participant medical record. See the SoA for data to be collected at the time of discontinuation of study drug and follow-up and for any further evaluations that need to be completed.

Possible reasons leading to permanent discontinuation of study drug:

- **participant decision**
 - the participant requests to discontinue study drug
- **clinical considerations**
 - initiation of prohibited concomitant medications (see Section 6.5) if participants will not or cannot discontinue them
 - intolerable GI symptoms despite management as described in Section 6.5.1 and Section 6.6.1

Note: The investigator should contact the Sponsor CRP/CRS to discuss whether it is medically appropriate for the participant to continue study treatment.

- if the investigator, after consultation with the sponsor-designated medical monitor, determines that a systemic hypersensitivity reaction has occurred related to study drug administration, the participant should be permanently discontinued from the investigational drug
- BMI \leq 19 kg/m² is reached at any time during the treatment period
- diagnosis of T1D
- diagnosis of MTC or MEN2 after randomization
- significant elevation of calcitonin (Section 8.3.2.3.1)
- diagnosis of acute or chronic pancreatitis
- diagnosis of an active or untreated malignancy (other than basal or squamous cell skin cancer, in situ carcinomas of the cervix, or in situ prostate cancer) after randomization
- onset of pregnancy in a female participant

- occurrence of any other treatment-emergent AE (TEAE), SAE, or clinically significant finding for which the investigator believes that permanent study drug discontinuation is the appropriate measure to be taken
- PHQ-9 score ≥ 15

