 - Participants should be referred to a Mental Health Professional (MHP) to assist in deciding whether the participant should be discontinued from study drug. If a participant's psychiatric disorder can be adequately treated with psycho- and/or pharmacotherapy, then the participant, at the discretion of the Investigator (in agreement with the MHP), may be continued in the trial on randomized therapy.
- in addition, study drug may be discontinued if participants
 - answered "yes" to either Question 4 (Active Suicidal Ideation with Some Intent to Act, Without Specific Plan) on the "Suicidal Ideation" portion of the C-SSRS
 - or**
 - answered "yes" to Question 5 (Active Suicidal Ideation with Specific Plan and Intent) on the "Suicidal Ideation" portion of the C-SSRS
 - or**
 - answered "yes" to any of the suicide-related behaviors (Actual attempt, Interrupted attempt, Aborted attempt, Preparatory act or behavior) on the "Suicidal Behavior" portion of the C-SSRS.

Note: A psychiatrist or appropriately trained professional may assist in the decision to discontinue the participant.

- **discontinuation due to a hepatic event or liver test abnormality**
 - Participants who are discontinued from study drug due to a hepatic event or liver test abnormality should have additional hepatic safety data collected via eCRF.
 - Discontinuation of the study drug for abnormal liver tests **should be** considered by the investigator when a participant meets 1 of the following conditions after consultation with the Lilly-designated medical monitor:
 - ALT or AST $>8X$ ULN
 - ALT $>2X$ baseline value OR ≥ 300 U/L, whichever occurs first, if baseline ALT $\geq 2X$ ULN
 - ALT or AST $>5X$ ULN for more than 2 weeks
 - ALT or AST $>3X$ ULN and TBL $>2X$ ULN or international normalized ratio (INR) >1.5
 - ALT or AST $>3X$ ULN with the appearance of fatigue, nausea, vomiting, right upper-quadrant pain or tenderness, fever, rash, and/or eosinophilia ($>5\%$)

- ALP >3X ULN
- ALP >2.5X ULN and TBL >2X ULN
- ALP >2.5X ULN with the appearance of fatigue, nausea, vomiting, right-quadrant pain or tenderness, fever, rash, and/or eosinophilia (>5%).

Refer to Section 10.1.8 for discontinuation of specific sites or of the study as a whole.

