4.6.7.12.1. Patient Health Questionnaire

Total scores for the PHQ-9 range from 0 to 27 with total scores categorized as

- none (not depressed): 0 through 4
- mild: 5 through 9
- moderate: 10 through 14
- moderately severe: 15 through 19, and
- severe: 20 through 27.

Shift tables will be provided showing the counts and percentages of participants within each baseline category (maximum value) versus each postbaseline category (maximum value) by treatment.

Additionally, the following 3 outcomes of interest will be compared between treatments (based on the maximum value during baseline and postbaseline):

- any increase in depression category (ie, worsening of depression): includes participants in the none, mild, moderate, or moderately severe category during baseline and with at least 1 postbaseline measurement
- increase from No or Mild Depression to Moderate, Moderately Severe or Severe Depression: includes participants in the none or mild depression category during baseline and with at least 1 postbaseline measurement; and
- increase from Mild or Moderate Depression to Moderately Severe or Severe Depression: includes participants in the mild or moderate depression category during baseline and with at least 1 postbaseline measurement.

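### The SAP's only between-arm PHQ-9 comparison cut at 15 excludes participants scoring 0 to 4 at baseline, so their rises to the protocol's referral score are compared only when pooled with milder worsening

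*Protocol*

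**What the plan says.** **Protocol.** Section 8.3.2.13 lists "a PHQ-9 score ≥ 15" among the findings that lead to referral to a mental health professional. Section 7.1 puts "PHQ-9 score ≥ 15" among the possible reasons for permanent discontinuation of study drug and explains: "Participants should be referred to a Mental Health Professional (MHP) to assist in deciding whether the participant should be discontinued from study drug". It also allows the participant to continue on randomized therapy if the disorder can be adequately treated. The same score bars entry (Section 5.2): "Have a Patient Health Questionnaire-9 (PHQ-9) score of 15 or more at Visit 1".

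**SAP 4.6.7.12.1.** The total score is divided into five categories. The lowest is "none (not depressed): 0 through 4", followed by mild (5 to 9) and moderate (10 to 14). The first category at or above the protocol's score is "moderately severe: 15 through 19", and severe is 20 to 27. Shift tables of maximum baseline against maximum postbaseline category are planned by treatment. In addition, the "following 3 outcomes of interest will be compared between treatments":

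1. any rise in category, for baseline none, mild, moderate or moderately severe;
2. a rise to moderate or worse (10 or more), for baseline none or mild;
3. "increase from Mild or Moderate Depression to Moderately Severe or Severe Depression: includes participants in the mild or moderate depression category during baseline".

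Each requires at least one postbaseline measurement.

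**The concern.** A score of 15 or more is the level at which the protocol acts. Entry excludes that score at Visit 1, so the natural group at risk of newly reaching it is everyone below 15 at baseline: none, mild and moderate together. The third outcome takes only the last two. The second outcome does admit the none category, and the SAP gives no reason for leaving it out of the third.

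Participants without depressive symptoms at baseline are those in whom a score of 15 or more would represent new onset, and the protocol makes depression an adverse event of special interest (8.3.2). If the drug moved some of them to 15 or more, the one comparison set at that severity would show nothing. In outcome 1 a move from 3 to 20 counts the same as a move from 4 to 5, and in outcome 2 the same as a rise to 10.

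**Working it through.** The plan states no power or other figure for the PHQ-9 outcomes, so there is nothing to reproduce. The check has three parts.

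**Step 1. Upward shifts that end at 15 or more, against the three definitions.**

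| Baseline → postbaseline maximum | Outcome 1 | Outcome 2 | Outcome 3 |
|---|---|---|---|
| none → moderately severe or severe | event | event | excluded |
| mild → moderately severe or severe | event | event | event |
| moderate → moderately severe or severe | event | excluded | event |
| moderately severe → severe | event | excluded | excluded |

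Of the shifts that start below 15, only those from the none category are missing from the comparison cut at 15. Outcomes 1 and 2 count them, but outcome 1 also counts none → mild, none → moderate and mild → moderate, and outcome 2 also counts none → moderate and mild → moderate.

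**Step 2. Share of new scores of 15 or more that outcome 3 leaves out.**

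Let q be the proportion in the none category among those below 15 at baseline, and r their risk of reaching 15 or more relative to mild/moderate participants. Then

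share left out = q·r / (q·r + 1 − q).

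The documents give neither q nor r. Assumed ranges: q from 0.5 to 0.9, r from 0.05 to 1. The number randomized per dose is 300 × 2/10 = 60 (Protocol 9.2), so the outcome 3 denominator is at most about 60 × (1 − q).

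| q | Left out, r = 0.05 | Left out, r = 0.5 | Left out, r = 1 | r above which more than half is left out | Outcome 3 denominator, of 60 |
|---|---|---|---|---|---|
| 0.5 | 5% | 33% | 50% | 1.00 | 30 |
| 0.6 | 7% | 43% | 60% | 0.67 | 24 |
| 0.7 | 10% | 54% | 70% | 0.43 | 18 |
| 0.8 | 17% | 67% | 80% | 0.25 | 12 |
| 0.9 | 31% | 82% | 90% | 0.11 | 6 |

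Example: q = 0.8 and r = 0.5 give 0.40 / (0.40 + 0.20) = 67%. The fourth numerical column is (1 − q)/q.

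**Step 3. What pooling does to a contrast (assumed counts, 60 per arm, two-sided Fisher's exact test).**

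Suppose six participants on one dose move from none to 15 or more and none do on placebo.

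- Cut at 15, everyone below 15 at baseline included: 6 v 0, p = 0.027.
- Outcome 2, if each arm also has 6 milder events: 12 v 6, p = 0.20.
- Outcome 1, if each arm also has 12 milder events: 18 v 12, p = 0.29.
- Outcome 3 as written: contains none of the six.

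For simplicity the denominator is 60 throughout; outcome 2's would be smaller, because baseline-moderate participants are excluded. One event fewer at the 15 cut (5 v 0) gives p = 0.057.

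**The case against.** The strongest reply is that nobody is lost. Outcomes 2 and 3 together count every rise from below 15 to 15 or more: from none in outcome 2, from mild in both, from moderate in outcome 3. The shift tables give the same cells by arm, and adding the none, mild and moderate rows across the two top columns produces the proposed result by hand. Depression and suicidality adverse events are summarized by treatment whatever the baseline PHQ-9 (SAP 4.6.7.12), and C-SSRS results by arm (SAP 4.6.7.12.2). Referral at 15 applies to everyone, so individual safety does not depend on this table. With about 60 per arm, a formal test needs 6 v 0 to fall below 0.05.

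All of that is correct, and it limits the point to granularity at the action threshold. It does not remove it. Outcomes 1 and 2 cannot separate a severe shift from a mild one, no comparison is specified for the shift-table cells, and the adverse event search depends on what is reported as an event.

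Two stronger readings are tempting and should not be made. A reader might infer that most new scores of 15 or more go uncompared. That needs a baseline distribution and category-specific risks which the documents do not give: with q = 0.6 and r = 0.5 the omitted share is 43%. These shifts are, moreover, compared in outcomes 1 and 2. A reader might also infer that 15 or more means automatic stopping of study drug. Protocol 7.1 describes referral and a decision, with continuation allowed.

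**Conclusion.** The point holds in this limited form. By its stated population rule, the only PHQ-9 comparison cut at the protocol's referral score excludes participants scoring 0 to 4 at baseline. Their shifts to 15 or more are compared between arms only when mixed with milder worsening, and are otherwise only tabulated. This follows from the text and needs no assumption.

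The size does need assumptions. The omitted share of new scores of 15 or more is about 5% to 90% over the ranges above, and no narrower figure can be defended from the documents. Nothing here affects the primary analysis or the care of individual participants. It is an inexpensive improvement to a safety comparison.

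**What to change.** In SAP 4.6.7.12.1, redefine the third outcome, or add a fourth, as: maximum baseline score below 15 (none, mild or moderate) to maximum postbaseline score of 15 or more, with all such participants who have at least one postbaseline measurement in the denominator. Keep the present mild/moderate version as a sub-row.

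Under the assumed q, the denominator rises from about 6 to 30 per dose to about 60, less anyone at 15 or more at baseline or without a postbaseline score. The change uses scores already collected and costs one extra table row. Because events are likely to be few, counts and percentages by arm should carry the interpretation, with any p-value as descriptive support.
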